6.5 Critical Structures

6.5.1 Critical Organ Dose-Volume Limits

The following table lists maximum dose limits to a point or volume within several critical organs. These are absolute limits, and treatment delivery that exceeds these limits will constitute a major protocol violation (See Section 5.7). The dose is listed as total over 5 fractions and per fraction.

These limits were formulated with the approval of the study committee using known tolerance data, radiobiological conversion models, norms used in current practice at academic centers. Participating centers are encouraged to observe prudent treatment planning principles in avoiding unnecessary radiation exposure to critical normal structures irrespective of these limits.

In order to verify each of these limits, the organs must be contoured such that appropriate dose volume histograms can be generated. Instruction for the contouring of these organs will follow below.

Organ	Volume	Dose (cGy)
Spinal Cord	Maximum point dose	22 Gy (4.4 Gy per fraction)
	Less than 8 cc	20 Gy (4 Gy per fraction)

Cauda Equina	Maximum point dose	27.5 Gy (5.5 Gy per fraction)
	Less than 10 cc	25 Gy (5 Gy per fraction)
Sacral Plexus	Maximum point dose	30 Gy (6 Gy per fraction)
	Less than 10 cc	27.5 Gy (5.5 Gy per fraction)
Peri-prostatic Anterior rectal wall	Maximum point dose	No more than 105% of the prescription dose
Peri-prostatic Lateral rectal walls	Maximum point dose	No more than 100% of the prescription dose
	Less than 3 cc cumulative (both sides)	No more than 90% of the prescription dose
Peri-prostatic Posterior rectal wall and anus	Maximum point dose	No more than 45% of the prescription dose
Rectum superior to prostate	Maximum point dose	30 Gy (6 Gy per fraction)
	Less than 10 cc	25 Gy (5 Gy per fraction)
Small intestine	Maximum point dose	29 Gy (5.8 Gy per fraction)
	Less than 10 cc	19.5 Gy (3.9 Gy per fraction)
Prostatic urethra	Maximum point dose	No more than 105% of prescription dose
Bladder	Maximum point dose	No more than 105% of prescription dose
	Less than 10 cc	18.3 Gy (3.65 Gy per fraction)
Penile bulb	Maximum point dose	No more than 100% of prescription dose
	Less than 3 cc	30 Gy (6 Gy per fraction)
Femoral heads	Less than 10 cc cumulative (both sides)	30 Gy (6 Gy per fraction)
Skin within fold (e.g., the gluteal fold)	Maximum point dose	20 Gy (4 Gy per fraction)
Skin not within fold	Maximum point dose	27.3 Gy (5.45 Gy per fraction)
Seminal Vesicles	No dose constraint	Collect dose statistics for documentation only

6.5.2 Contouring of Normal Tissue Structures

6.5.2.1 Spinal Cord

The spinal cord will be contoured as one structure based on the bony limits of the spinal canal. The spinal cord should be contoured anywhere it is visualized in the treatment plan (typically superior to L2).

6.5.2.2 Cauda Equina

The cauda equina will be contoured as one structure based on the bony limits of the spinal canal. The cauda equina should be contoured starting superiorly at the bottom of the spinal cord (typically around L2 and terminal at the inferior extent of the thecal sac (typically at S3).

6.5.2.3 Sacral Plexus

The left and right sacral plexus will be contoured collectively as one structure. The location of the sacral plexus will be approximated by contouring the space defined medially by the sacral foramina from S1-S3 including contouring within the sacral foramina, posteriorly along the limits of the true pelvis, laterally to 2-3

cm lateral to the sacral foramina, and anteriorly about 3-5 mm from the posterior limits of the countour.

6.5.2.4 Peri-prostatic Rectal wall
 The circumference of the rectum adjacent to the prostate will be divided into 4 equal quadrants (anterior, left lateral, right lateral, and posterior). Assigning 0 degrees at the most anterior aspect of the rectum at the mid sagittal plane, the dividing lines between each quadrant will occur at 45, 135, 225, and 315 degrees. The right and left lateral walls will be combined into a single structure. Only the rectal wall will be included in these contours, not the contents of the lumen. Patients will be treated with a rectal balloon filling the lumen which should therefore not be included in the contours.

6.5.2.4.1 Anterior Peri-prostatic Rectal Wall
 Starting inferiorly just above the anal sphincter, the anterior quadrant of the rectal wall (from 315 to 45 degrees) should be contoured (absent the lumen) up to 1 cm above the superior extent of the prostate.

6.5.2.4.2 Lateral Peri-prostatic Rectal Wall
 Starting inferiorly just above the anal sphincter, the lateral quadrant of the rectal wall (from 45 to 135 degrees and also from 225 to 315 degrees) should be contoured (absent the lumen) up to 1 cm above the superior extent of the prostate. These two structures should be combined as a single structure for purposes of dose volume analyses.

6.5.2.4.3 Posterior Peri-prostatic Rectal Wall
 Starting inferiorly just above the anal sphincter, the posterior quadrant of the rectal wall (from 135 to 225 degrees) should be contoured (absent the lumen) up to 1 cm above the superior extent of the prostate.

6.5.2.5 Rectum Superior to Prostate
 Starting inferiorly at the superior extent of the Peri-prostatic Rectal Wall described above, the entire wall and lumen of the rectum should be contoured up to the level of the sacral promontory.

6.5.2.6 Small Intestine
 The small intestines should be contoured as a conglomerate of all bowel loops within each CT cut starting at the first appearance of small intestine in the pelvis and extending superiorly up to the level of the sacral promontory within each cut.

6.5.2.7 Prostatic Urethra
 The prostatic urethra will be identified by the urethral catheter plus 1-2 mm of tissue radially into the prostate. The inferior aspect of the prostatic urethra coincides with the apex of the prostate (urethograms may be helpful in identifying the apex). The superior aspect of the prostatic urethra coincides with the base of the prostate at the bladder inlet.

6.5.2.8 Bladder
 The bladder should be contoured in its entirety absent its contents. As such, only the wall of the bladder is included in the dose volume analysis. The bladder wall may be approximated by contouring the outer outline of the entire bladder and subtracting this volume from the same volume minus 0.5 cm in all directions (to define the inner surface of the bladder).

6.5.2.9 Penile Bulb
 The penile bulb will be contoured starting superiorly at the inferior aspect of the pelvic diaphragm (urethral sphincter) and extending inferiorly and anteriorly up to 3 cm.

6.5.2.10 Femoral heads
 The femoral heads will be contoured bilaterally as one structure.

6.5.2.11 Skin

The skin will constitute the external contour minus 5 mm. The skin within folds, especially in the gluteal folds as the skin surfaces make contact, will be contoured as a separate structure.

6.5.2.12 Seminal vesicles

The seminal vesicles should be contoured right and left as one structure. There is no protocol dose constraint for these structures, but they will be contoured to collect dose deposition data.

6.5.2.13 Anus

Anus will be contoured as one structure starting just inferior to rectum.

6.6 Documentation Requirements

6.6.1 In general, treatment interruptions should be avoided by preventative medical measures and nutritional, psychological, and emotional counseling. Treatment breaks, including indications, must be clearly documented on the treatment record.

6.7 Compliance Criteria

6.7.1 Accreditation Compliance

All criteria listed in Section 5 must be completed to the satisfaction of the study committee in order to be accredited. Upon completion of the criteria, a letter will be sent to institutions' PIs informing them of accreditation for the study. No institution will be allowed to enroll patients without accreditation.

6.7.2 Dosimetry Compliance

Section 6 describes appropriate conduct for treatment planning dosimetry. Criteria for both major and minor deviations are provided in the table in Section 6.4. In addition to the criteria in section 6.4, the table in Section 6.5 lists dose volume limits for specific organs and structures. Exceeding these limits by more than 2.5% constitutes a minor protocol violation. Exceeding these limits by more than 5% constitutes a major protocol violation.

6.7.3 Treatment Delivery Compliance

Set-up films will be compared to digitally reconstructed radiographs from the same beam's eye view. Deviations of less than 0.5 cm will be considered compliant. Deviations from 0.5-0.75 cm will be considered minor protocol deviations. Deviations greater than those listed as minor will be considered major protocol deviations.

6.8 R.T. Quality Assurance Reviews

[name], along with a medical physicist, will perform an RT Quality Assurance Review after complete data for the first 20 cases enrolled has been received at the University of Texas Southwestern. They will perform the next review after complete data for the next and subsequent 20 cases enrolled has been received at the University of Texas Southwestern. The final cases will be reviewed within 3 months after this study has reached the target accrual or as soon as complete data for all cases enrolled has been received, whichever occurs first.

6.9 Radiation Adverse Events

6.9.1 Gastro-intestinal

Monitored treatment related toxicity associated with gastrointestinal function will include colitis, dehydration, diarrhea, enteritis, fistula, nausea, vomiting, obstruction, proctitis, fecal incontinence, stricture/stenosis, hemorrhage, and

ulcer. The consequences of gastro-intestinal toxicity should all be graded according to the Common Terminology Criteria For Adverse Events (CTCAE).

6.9.2 Renal/Genitourinary/Sexual/Reproductive

Monitored treatment related toxicity associated with renal and genito-urinary function will include cystitis, fistula, urinary incontinence, urinary obstruction, stricture/stenosis, hemorrhage, and urinary retention. Monitored treatment related toxicity associated with sexual and reproductive function will include erectile dysfunction and ejaculatory dysfunction. The consequences of renal/genitourinary/sexual and reproductive toxicity should all be graded according to the Common Terminology Criteria For Adverse Events (CTCAE). In addition, patients will fill out the AUA scoring sheets reflecting basic urinary function at regular intervals according to the study calendar in Appendix VI.

6.9.3 Neurology

Monitored treatment related toxicity associated with neurology function will include myelitis, motor and sensory neuropathy, plexopathy, and pain. The consequences of neurology toxicity should all be graded according to the Common Terminology Criteria For Adverse Events (CTCAE).

6.9.4 Constitutional Symptoms

Monitored treatment related toxicity associated with constitutional function will include fatigue, fever, and weight loss. The consequences of constitutional toxicity should all be graded according to the Common Terminology Criteria For Adverse Events (CTCAE).

6.9.5 Skin

Monitored treatment related toxicity associated with skin function will include fibrosis, rash (desquamation), ulceration, and telangiectasia. The consequences of skin toxicity should all be graded according to the Common Terminology Criteria For Adverse Events (CTCAE).

6.9.6 Quality of Life and Other Toxicities

Other treatment related toxicity attributed to the therapy will be captured, recorded and the consequences of should all be graded according to the Common Terminology Criteria For Adverse Events (CTCAE). Quality of life after prostate cancer treatment will be assess using the Expanded Prostate Cancer Index Composite (EPIC) formalism [41]. Validation and description of this scale can be found at the website:
<http://roadrunner.cancer.med.umich.edu/epic/epicmain.html>

6.10 Serious Adverse Event Reporting

6.10.1 ERGO

Electronic Research Grant Organizer (ERGO) constitutes a mechanism for reporting serious adverse events to the UTSW IRB for reporting purposes.

Any adverse event equivalent to CTCAE V.3 grade 3, 4, or 5 or which precipitates hospitalization or prolongs an existing hospitalization must be reported regardless of designation (expected or unexpected) along with the attribution. This includes all deaths that occur within 30 days after the patient was discontinued from the study regardless of attribution AND any events that occur beyond 30 days and are considered probably related to treatment.

Participating sub-sites must file an SAE report (the CRF plus information describing the event, the grade, and the attribution) within 48 hours of the investigator's awareness of the occurrence of the event.

Attribution of an event can be categorized as:

- Not Related
- Possibly Related
- Likely Related

Adverse events (below grade 3) do not need to be submitted immediately. Rather, they should be documented in the Adverse Events CRF along with a brief description of the event, grade, and attribution).

All SAE reports should be made via FAX transmission to:

**Department of Radiation Oncology
Clinical Research Office
The University of Texas Southwestern Medical Center
Attention: [name], Project Manager
[contact]**

7.0 DRUG THERAPY

Not applicable to this trial.

8.0 OTHER THERAPY

8.1 Permitted Supportive Therapy

All supportive therapy for optimal medical care will be given during the study period at the discretion of the attending physician(s) within the parameters of the protocol and documented on each site's source documents as concomitant medication.

- 8.1.1 Obstructive flow medicines (alpha blockers) 5 alpha reductase inhibitors)
- 8.1.2 Antiemetics
- 8.1.3 Anticoagulants
- 8.1.4 Antidiarrheals
- 8.1.5 Analgesics
- 8.1.6 Hematopoietic Growth Factors
- 8.1.7 Herbal products
- 8.1.8 Nutritional supplementation

9.0 SPECIMEN SUBMISSION

9.1 Specimen Investigational Nature

Initially serum will be collected in order to build proteomic profiles of treatment response, however, with time there may be other analytical methodologies that are not yet devised. Blood cells will be processed and RNA and DNA collected. Ultimately, gene expression and genotyping will be performed and correlated with treatment outcome or normal tissue response.

9.2 Specimen Collection for Translational Research

- Serum will be collected and frozen for subsequent analysis for patients who choose to participate
- 9.3 Whole blood will be drawn [20 ml per collection timepoint: 10 ml from red top and 10 ml from lavender top tubes] using standard procedure in order to collect lymphocytes as well as plasma serum. Blood will be processed using standard procedure immediately after it is collected and then stored at -70 to -80 degrees C. The samples will be kept indefinitely or until exhausted.

9.3.1 Collection Timepoints

1. Within 1 week prior to the first treatment (baseline)
2. Immediately after the first treatment
3. Immediately before the second treatment (approximately 48-72 hours after the first treatment)
4. Immediately after the fifth treatment
5. 6 months after completing the fifth treatment

9.3.2 A Pathology Report from the pretreatment core biopsy describing the original tumor specimen is required. The patient's name and/or other identifying information should be removed from the report. The surgical pathology numbers and information must NOT be removed from the report.

9.3.3 For serum collection, the following materials must be provided: the date of collection of the serum, timepoint of blood collection, type of sample, the protocol number, and the patient's study specific study-ID number.

9.3.4 Submit materials for Translational Research to:
[name].
UT Southwestern Medical Center at Dallas
[name]
[contact]
[contact]

9.4 Confidentiality/Storage

9.4.1 Upon receipt, the specimen is labeled with the protocol number and the patient's assigned study-identification number only. The database only includes the following information: the number of specimens received, the date the specimens were received, documentation of material sent to a qualified investigator, type of material sent, and the date the specimens were sent to the investigator. No clinical information is kept in the database.

9.4.2 Specimens for translational research will be stored for an indefinite period of time (or until exhausted) and may be used for future studies. If at any time the patient withdraws consent to store and use specimens, the material will be returned to the institution that submitted it.

9.4.3 Specimen will be stored at the UT Southwestern Medical Center Division of Molecular Radiation Biology laboratories (NC 7.206) and the UT Southwestern Tissue Repository.

10.0 PATIENT ASSESSMENTS

10.1 Study Parameters: See Appendix II.

10.2 Follow-up Schedule

10.2.1 Initial follow-up visit at 1.5 months from the end of treatment.

10.2.2 After initial follow-up visit, follow-up will be done at 3, 6, 9, and 12 months post therapy.

10.2.3 Then every six months until three years post treatment.

10.2.4 Then annually for years 3-10.

10.2.5 A bone scan will be performed on any patient who presents with complaints of bone pain that cannot be attributed to any intercurrent disease. Discretionary plain films may be needed to evaluate lesions seen on bone scan to confirm the diagnosis of metastatic disease.

10.3 Criteria for Toxicity

10.3.1 All acute and late adverse events from protocol radiation therapy will be reported and scored for severity using the NCI Common Terminology Criteria for Adverse

Events (CTCAE) version 3.0. A copy of the CTCAE v3.0 can be downloaded from the CTEP home page (<http://ctep.info.nih.gov>).

Please note that this study will not be using separate toxicity scales for acute and late radiation adverse events.

10.4 Measurement of Response

10.4.1 Although not required, it is encouraged that prostate tumor dimensions in centimeters or grams be recorded on the data collection forms for the follow up evaluations. PSA levels should be obtained per study calendar.

10.4.2 After study entry, disease evaluations will be made and recorded using the following criteria:

10.4.2.1 No Evidence of Disease (NED): No clinical evidence of disease on digital rectal examination and no PSA failure.

10.4.2.2 Equivocal Disease (ED): This rating will be assigned under the following circumstances:

- 1) If abnormalities are present on the prostate digital rectal examination but are thought to be abnormal due to treatment and felt not to represent tumor.
- 2) If clinical evidence of residual tumor is present but this has regressed from a previous examination (initial registration).
- 3) PSA 2.1 - 4 ng/mL. Rebiopsy is required, before starting hormone therapy, in any patient with PSA failure but with negative bone scan and CT scans. If the biopsy is negative, then they will be scored as NED.

10.4.2.3 Progressive Disease (PD): Progressive disease will be declared if one or more of the following criteria are met:

- 1) Clinical evidence in the prostate gland of disease progression or recurrence.
- 2) Clinical or radiographic evidence of tumor recurrence within the pelvic lymphatics or soft tissue beneath the bifurcation of the common iliac arteries,
- 3) Clinical or radiographic evidence of hematogenous (osseous, hepatic, etc.) and/or extrapelvic lymphatic or soft tissue relapse.

10.5 Other Response Parameters

10.5.1 Disease-Free Interval: The disease-free interval will be measured from the date of accession to the date of documentation of progression or until the date of death (from other causes).

10.5.2 Time to Biochemical Failure: The RTOG-ASTRO definition (also known as the Phoenix definition) of PSA failure will be used. Thus, when the PSA rises by more than 2 ng/ml above the lowest level (nadir) achieved after treatment, biochemical failure has occurred and the date of the failure is recorded at the time the nadir plus 2 ng/ml level is reached.

10.5.3 Time to Local Progression: The time to progression will be measured from the date of study entry to the date of documented local progression as determined by clinical exam.

10.5.4 Time to Distant Failure: The time to distant failure will be measured from the date of study entry to the date of documented regional nodal recurrence or distant disease relapse. Patients with evidence of biochemical failure, but a negative prostate biopsy, will be considered as distant failure only.

10.5.5 Overall Survival: The survival time will be measured from the date of accession to the date of death. All patients will be followed for survival. Every effort should be made to document the cause of death.

10.5.6 Disease-Specific Survival Disease-specific survival will be measured from the date of study entry to the date of death due to prostate cancer. The following will be considered as failure events in assessing disease specific survival:

- Death certified as due to prostatic cancer.
- Death from other causes with active malignancy (clinical or biochemical progression).
- Death due to complications of treatment, irrespective of the status of malignancy.
- Death from other causes with previously documented relapse (either clinical or biochemical) but inactive at the time of death will not be considered in disease-specific survival, but will be analyzed separately.

10.5.7 Responsibilities of the Medical Monitor:

The medical monitor is required to review all unanticipated problems involving risk to subjects or others, serious adverse events and all subject deaths associated with the protocol and provide an unbiased written report of the event. At a minimum, the medical monitor must comment on the outcomes of the event or problem and in case of a serious adverse event or death, comment on the relationship to participation in the study. The medical monitor must also indicate whether he/she concurs with the details of the report provided by the principal investigator. Reports for events determined by either the investigator or medical monitor to be possibly or definitely related to participation and reports of events resulting in death must be promptly forwarded to the USAMRMC ORP HRPO.

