2.0 OBJECTIVES

- 2.1 In phase I, the primary objective is to escalate the dose of stereotactic radiotherapy to a tumorcidal dose without exceeding the maximum tolerated dose in patients with organ confined prostate cancer.
- 2.2 In phase I, a secondary objective is to determine the dose-limiting toxicity (if the maximum tolerated dose is reached).
- 2.3 In phase II, the primary objective is to determine the late severe grade 3-5 GU and GI toxicity from 270-540 days (i.e., 9-18 months) from the start of the protocol treatment. It is graded based on CTCAE v3.0.
- 2.4 In phase II, secondary objectives will be to determine the 2 year biochemical (PSA) control (freedom from PSA failure), disease free and overall survival, local control, freedom from distant metastases, and the incidence of high grade adverse events of any type from the therapy in the treated patients in order to determine if the therapy is promising enough for further clinical investigation.

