13.2.2 Secondary Endpoints

- Acute severe GU and GI toxicity is defined as grade 3-5 toxicity occurring prior to 270 days from the start of protocol treatment. It is graded based on CTCAE v3.0.
- Non GU and GI toxicity.
- Biochemical failure RTOG-ASTRO definition (also known as Phoenix definition) - Thus, when the PSA rises by more than 2 ng/ml above the lowest level (nadir) achieved after treatment, biochemical failure has occurred and the date of the failure is recorded at the time the nadir plus 2 ng/ml level is reached.
- Overall survival
- Disease-specific survival
- Clinical progression including local/regional and distant relapse

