13.4 Patient Accrual and Study Duration

13.4.1 It is expected that it will take approximately three to five years to complete the study. The analysis for late toxicity will be carried out after each patient has had at least 270 days (i.e., 9 months) of follow-up from the end of the acute period, a total of 540 days (i.e., 18 months) of follow-up. For the secondary endpoint of biochemical failure, an additional 18 months of follow-up are needed to estimate the 3-year failure rate. Study-related data will be stored for 5 years after termination of the study when accrual is no longer taking place and all patients have discontinued follow-up procedures. Blood drawn for translation research will be kept indefinitely or until exhausted.

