13.5 Analysis Plan

Interim Reports: Interim reports will be prepared every six months until the results of the study are published. In general, the interim reports will contain information about patient accrual rate with projected completion dates of the trial, status of QA review and compliance rate of treatment per protocol, and the frequencies and severity of toxicity.

13.5.2 *The Analysis of Severe Late GU/GI Toxicity:* This analysis will be carried out when each patient has had at least 270 days (i.e., 9 months) of follow-up after the end of the acute period, a total of 540 days (i.e., 18 months) of follow-up. The time to the occurrence of severe late GU/GI toxicity is defined as the time interval from start of protocol treatment to the date of onset of grade 3-5 GU/GI toxicity. The time analysis for recording severe late GU/GI toxicity for this protocol will be limited to 540 days from start of protocol therapy. If no such toxicity is observed before the time of the analysis, the patient will be censored at the time of the analysis. The hazard rate will be estimated by the life table approach with a time span of 18 months. The one-sided Z-test will be used to test the significance of the difference between the logarithm of the observed hazard rate and the logarithm of the hypothesized hazard rate of 0.006/month with variance equal to the reciprocal of the number of cases with late toxicity observed. Because of the lead time of 9 months for the acute period, the 18-month late toxicity will be estimated by the 9-month toxicity rate using the cumulative incidence approach [37] to the defined time to severe late GU/GI toxicity.

13.5.3 *Estimation of Secondary Endpoints Related to the Efficacy:* Cumulative incidence approach [37] will be used to estimate the failure rate for biochemical, disease-specific, local-regional and distant failures. Kaplan-Meier method [38] will be used to estimate the overall survival rate.

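### Biochemical failure is nadir + 2 ng/ml alone, with no rule for salvage treatment started earlier, so the PSA control rate can be overstated by about 2 points per such man

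*Combined protocol and SAP*

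**What the plan says.** Section 10.5.2 adopts the RTOG-ASTRO (Phoenix) definition and spells it out as a single criterion: "when the PSA rises by more than 2 ng/ml above the lowest level (nadir) achieved after treatment, biochemical failure has occurred". Section 13.2.2 repeats it for phase II and dates the event: "the date of the failure is recorded at the time the nadir plus 2 ng/ml level is reached". Neither section mentions treatment given after SBRT.

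For the analysis, section 13.5.3 says: "Cumulative incidence approach [37] will be used to estimate the failure rate for biochemical, disease-specific, local-regional and distant failures". It lists no competing events and no censoring rule for biochemical failure.

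Section 2.4 asks for 2-year PSA control, as one of several secondary outcomes used to judge whether the therapy deserves further study. Section 13.4.1 instead refers to a later time point: "an additional 18 months of follow-up are needed to estimate the 3-year failure rate". The gap described here is the same at either landmark.

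Three other places bear on the point:

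- Section 10.4.2.2 contains the only text on hormone therapy started after SBRT: "Rebiopsy is required, before starting hormone therapy, in any patient with PSA failure but with negative bone scan and CT scans".
- Section 10.4.2.3 gives three grounds for progressive disease: clinical progression in the gland, pelvic nodal or soft-tissue recurrence, and blood-borne or extrapelvic relapse. None uses PSA.
- Section 3.7 excludes men with planned adjuvant treatment. It is an entry condition, not a rule for treatment of relapse during follow-up.

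**The concern.** A man whose relapse is found clinically or on imaging, at a PSA still within 2 ng/ml of nadir, may start salvage treatment. If that treatment is hormonal, his PSA should fall. The protocol itself relies on this effect when it takes the eligibility PSA before any hormonal therapy (section 3.5 and the first note to Appendix I). He may then never cross nadir + 2 before the landmark.

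Under the stated definition he has no biochemical failure, although he was treated because the cancer came back. At stake is the PSA control rate in section 2.4. The phase II group is at most 50 men, so a single classification is visible in the reported percentage.

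**Working it through.** **No figure to reproduce.** The documents give no expected rate, precision target or sample size for PSA control. The check therefore compares ways of coding the same men.

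**Inputs**

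- n = 50 phase II patients, or 47 before the allowance for ineligible and missing cases (section 13.3.2).
- f = men who reach nadir + 2 by the landmark. Not in the documents; assumed 2 or 5.
- s = men who start salvage before the landmark without having reached nadir + 2, and do not reach it afterwards by the landmark. Not in the documents; assumed 0 to 5.

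**Formulas for the control rate, taking follow-up as otherwise complete**

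- A. Salvage ignored, definition read as written: 1 − f/n. Coding salvage as a competing event and reporting one minus the cumulative incidence of nadir + 2 gives the same value.
- B. Censored at the start of salvage, in the extreme case where every salvage start precedes every PSA failure: 1 − f/(n − s). Later censoring lies between B and A.
- C. Start of salvage counted as failure: 1 − (f + s)/n.

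The excess of A over C is s/n whatever the value of f: 1/50 = 2.0 points and 1/47 = 2.1 points per man; 5/50 = 10.0 points and 5/47 = 10.6 points for five men.

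**Example, n = 50 and f = 5 (percent)**

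| s | A | B | C | A − C | B − C |
|---|---|---|---|---|---|
| 0 | 90.0 | 90.0 | 90.0 | 0.0 | 0.0 |
| 1 | 90.0 | 89.8 | 88.0 | 2.0 | 1.8 |
| 2 | 90.0 | 89.6 | 86.0 | 4.0 | 3.6 |
| 3 | 90.0 | 89.4 | 84.0 | 6.0 | 5.4 |
| 5 | 90.0 | 88.9 | 80.0 | 10.0 | 8.9 |

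Over both values of n and both values of f, the excess under censoring is 1.8 to 2.0 points for one man and 8.9 to 10.1 points for five. Censoring removes little of the bias because these men are not a random sample of those still at risk: they leave because of relapse.

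**Can s be above zero under the protocol?** Yes. Section 10.4.2.3 declares progression without PSA. Section 10.2.5 prompts a bone scan for unexplained bone pain, and a note to Appendix I prompts one at suspected progression as well as at PSA failure. The protocol thus provides for relapse found by routes other than PSA.

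**The case against.** The case on the other side has real substance.

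- **The coding is not stated.** A reader might infer that the plan counts an early-salvaged man as PSA-controlled. No section says so; he could be censored or made a competing event. This limits the claim to what follows from the definition as written. It does not remove the bias, since the alternatives give the same or nearly the same rate.
- **The equivocal PSA band.** A reader might infer that men rated equivocal at PSA 2.1 to 4 ng/ml will be treated there and escape the definition. Some values in that band are below nadir + 2: a nadir of 1.5 and a PSA of 3.4 is a rise of 1.9. But section 10.4.2.2 gives a disease rating and does not say that treatment starts there. Its mention of hormone therapy concerns men who already have PSA failure. The point therefore rests on clinical or radiographic progression, not on this band.
- **Other endpoints catch clinical relapse.** A reader might infer that treatment failures become successes for the trial as a whole. They do not. Progressive disease counts toward the disease-free interval (10.5.1), local progression (10.5.3) or distant failure (10.5.4), and section 13.2.2 lists clinical progression separately. The distortion is in the PSA control rate.
- **PSA control is not ranked first.** Section 2.4 names it first in a list of secondary objectives but gives it no priority.
- **The number may be small or zero.** The HDR monotherapy update cited in section 1.5 reports 98% PSA control at 3 years in 65 men, about 1 failure per 50 (2% × 50). That is one series with another technique, so it does not settle the matter, but it argues against assuming several early-salvage men.
- **PSA alone is a coherent endpoint.** A purely biochemical measure beside separate clinical endpoints is defensible, and a composite brings in a treatment decision. Even so, the plan would have to say what happens to PSA values after salvage starts, and it does not.

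**Conclusion.** The gap stands as a cheap improvement to a secondary endpoint. Both definitions rest on nadir + 2 alone, and no rule covers salvage started earlier. Relative to counting such men as failures, the PSA control rate can be overstated by 2.0 points per man with n = 50, or 2.1 with n = 47. The excess is nearly the same, at 1.8 to 2.0 points, if one man is censored at salvage.

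The total depends on a count that the documents do not give. For an assumed 0 to 5 men it runs from 0 to about 10 points, and with none the rate is unchanged. It would be going too far to say that the rate is overstated; it can be. The per-man figure also assumes that the man does not cross nadir + 2 later but before the landmark.

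The primary late-toxicity test and the sample size of 50 do not depend on this endpoint.

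**What to change.** In sections 10.5.2, 13.2.2 and 13.5.3:

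1. Define biochemical failure as the earlier of a PSA more than 2 ng/ml above nadir and the start of any salvage treatment for prostate cancer, dated at that start.
2. Name death without failure as the competing event.
3. Report nadir + 2 alone as a sensitivity analysis, so that the purely biochemical rate remains visible.
4. Record the start date and reason for salvage at follow-up. Section 11.1 and Appendix I list no such item, but the case report forms are not shown, so it may already be collected.

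This classifies outcomes and changes nobody's treatment. The cost is a few sentences and, if not already present, two data fields. The downside is that the endpoint becomes a composite that includes a treatment decision, and the reported control rate may be slightly lower. Sections 10.5.4 and 10.5.6 also use biochemical status, so the text should say which version of the event feeds them.
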